2.5.1 Statistical hypothesis, model, and method of analysis

The study research hypothesis is that each investigated anti-inflammatory agent provides an improvement over placebo in NTB response at 24 weeks.

The change from baseline in NTB total z-score will be analyzed using a restricted maximum likelihood (REML)-based mixed model with repeated measurements (MMRM). The model will include fixed, categorical effects of treatment, visit, and treatment-by-visit interaction, as well as the continuous fixed covariates of baseline and baseline-by-visit interaction. Unstructured covariance will be used to model within-patient errors, with Kenward-Roger approximation to estimate denominator degrees of freedom. If the unstructured covariance causes model convergence issues, then other simpler covariance structures will be considered. Least squares mean, the associated 2-sided 90% confidence interval and the p-value will be obtained for each treatment at each visit. The primary comparison will be the contrast between active treatment and placebo at 24 weeks. Both cohort-wise and combined cohort analysis (i.e., pooling placebo data across different cohorts) will be performed.

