**Table 8-1 Assessment Schedule**

Commercially Confidential Information

Inclusion / Exclusion criteria	X	X										
Physical Examination/Neurological Examination	S		S	S		S		S	S	S	S	
Smoking and alcohol history	S											
Alcohol Test and Drug Screen	S											
Pregnancy and assessments of fertility	S	S		S		S		S	S	S	S	S
Hepatitis and HIV Screen	S											
Tuberculosis test	S											S
Demography	X											
Medical history/current medical conditions	X	X	X			X		X	X	X	X	X

Period	Screening		Treatment								End of Cohort		Safety Follow-Up		
Visit Name	Screening	Baseline	Initial Dose Day	Step-Up Visit		Treatment	Step-Up Visit	Treatment		End of Cohort Visit (EOC1) for All Molecules	End of Cohort Visit (EOC2) for Large Molecules Only - Extended Safety Visit	Early Termination Visit (Only when discontinuation from treatment/study occurs. See Section 9.)			
Days	-60 to -8	-7 to -1	1	8 ±1	15 ±1	22 ±1	29 ±2	36 ±1	57 ±2	85 ±3	113 ±2	141 ±2	171 -0 +2	281 ±2	30 days post last dose
Body Height	X														
Vital signs and body measurements	X	X	X	X	X	X	X	X	X	X	X	X	X	X	
AEs/SAEs	X	X	X	X	X	X	X	X	X	X	X	X	X	X	
Concomitant medications	X	X	X	X	X	X	X	X	X	X	X	X	X	X	
Electrocardiogram (ECG)	X		X	X					X			X	X	X	
Blood collection CCI	X														
Hematology	X	X		X		X		X	X	X	X	X	X	X	
Clinical Chemistry	X	X		X		X		X	X	X	X	X	X	X	
Urinalysis	X	X		X		X		X	X	X	X	X	X	X	

Commercially Confidential Information

Period	Screening		Treatment								End of Cohort		Safety Follow-Up		
Visit Name	Screening	Baseline	Initial Dose Day	Step-Up Visit		Treatment	Step-Up Visit	Treatment		End of Cohort Visit (EOC1) for All Molecules	End of Cohort Visit (EOC2) for Large Molecules Only - Extended Safety Visit	Early Termination Visit (Only when discontinuation from treatment/study occurs. See Section 9.)			
Days	-60 to -8	-7 to -1	1	8 ±1	15 ±1	22 ±1	29 ±2	36 ±1	57 ±2	85 ±3	113 ±2	141 ±2	171 -0 +2	281 ±2	30 days post last dose
Everyday Cognition Scale - Study Partner		X						X	X				X	X	
Neuropsychiatric Inventory - Caregiver Distress Scale		X					X		X	X			X		
Neuropsychological Test Battery	X	X					X		X	X		X	X		
Digit Symbol Substitution CCI	X	X					X		X	X		X	X		

Commercially Confidential Information

eCognitive At-Home Participant Assessment		2 times per week at baseline leading up to Day 1; 2 times per week in the week preceding Day 57; 2 times per week in the week preceding Day 85					

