The NTB is a composite of multiple globally-established neuropsychological tests that provide a thorough assessment of the cognitive domains affected by early AD, in particular, memory, executive function attention and verbal fluency. In comparison the ADAS-Cog and RBANS lack comprehensive measures of executive function ([Harrison et al 2007](#); [Garcia et al 2008](#)).

The NTB has shown good assay sensitivity to symptomatic treatment effects in AD drug intervention trials where other endpoints have failed ([Karin et al 2014](#); [Gilman et al 2005](#)).

Because inflammation has been strongly associated with executive function and memory, EXPLAIN-AD will include two additional executive tests of function; the Digit Symbol Substitution Test (DSST) CCI .

The DSST CCI are often classified as measures of executive function although in reality they can be regarded as measuring a number of cognitive functions ([Harrison 2018](#); CCI ). The DSST has previously detected beneficial treatment effects in MCI when other endpoints have failed ([Winblad et al 2008](#))

Commercially Confidential Information

Day-to-day variability in cognitive performance is an important yet under recognized feature of AD that may affect the accuracy of single-time point cognitive assessments ([Zettergren et al 2011](#)). EXPLAIN-AD will deploy at-home eCognitive testing in order to allow more frequent monitoring in more natural settings. These well-established and validated computerized tests CCI are brief and repeatable and provide a reliable assessment of cognitive processes that cannot easily be obtained through conventional paper-pencil tests. Moreover, studies suggest that increasing assessment frequency may improve detection of drug treatment effects on cognition ([Jaeger et al 2011](#)).

The ECog scale measures cognitively-relevant every day and complex abilities relevant to early AD ([Farias et al 2008](#)). Measuring changes in complex ADLs has important advantages as it may more closely reflect how individuals are functioning in the real world. An effect on measures of complex ADLs after an intervention has therefore ecological validity and is highly clinically relevant to participants and caregivers ([Weintraub et al 2018](#)).

Commercially Confidential Information

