## 12.8 Sample size calculation

### 12.8.1 Primary endpoint(s)

For the primary endpoint, change in NTB total z-score at week 24, data from 36 evaluable participants per arm (investigational agent and placebo) provides ~80% power to detect a statistically significant difference between the two groups at a 1-sided  $\alpha=0.10$  when the true standardized mean difference is 0.5. The effect size of 0.5 corresponds a moderate treatment effect which is thought to represent a clinically meaningful improvement at 24 weeks. To account for 15% dropout rate, approximately n=86 participants randomized in a 1:1 ratio would be needed to address the primary objective. These calculations take into account results of the published study by Frölich et al. (2019), where the standard deviation of the change in NTB total z-score was estimated to be ~0.38 for both active and placebo groups.

For smaller true effect sizes, the power is lower ([Table 12-1](#) below).

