2.5.4 Sensitivity analyses

To assess the robustness of the primary analysis results, several sensitivity analyses may be explored, using the primary model adjusted for several important baseline prognostic factors, such as age and educational level.

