2.5.5 Supplementary analyses

A supplementary analysis will be performed by averaging the screening and baseline visits to serve as new baseline, the visits at day 57 and Day 85 to serve as new day 85, and the last 2 visits (day 141 and Day 171) to serve as new Day171.

A supplementary analysis may involve estimation of treatment effects and contrasts (anti-inflammatory agent vs. placebo) within subgroups (e.g., MCI or mild AD positive versus negative) if the sample size in the subgroups is sufficient.

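### The primary NTB model leaves out the Screening NTB score; adding it as one covariate is likely to sharpen the week-24 contrast, modestly at the sample size reached

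*SAP*

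**What the plan says.** The primary model in SAP 2.5.1 is an MMRM on change from baseline in NTB total z-score. It has treatment, visit and their interaction, "as well as the continuous fixed covariates of baseline and baseline-by-visit interaction". The target is fixed: "The primary comparison will be the contrast between active treatment and placebo at 24 weeks".

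In Protocol Table 8-1 the row "Neuropsychological Test Battery" is marked at Screening (Day -60 to -8), at Baseline (Day -7 to -1), and then at Days 29, 57, 85, 141 and 171.

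The Screening score appears in SAP 2.5.5: "A supplementary analysis will be performed by averaging the screening and baseline visits to serve as new baseline". The same analysis averages Day 57 with Day 85, and takes "the last 2 visits (day 141 and Day 171) to serve as new Day171". SAP 2.6.7 repeats the scheme for secondary cognitive outcomes. The optional sensitivity analyses in SAP 2.5.4 adjust for "several important baseline prognostic factors, such as age and educational level"; Screening NTB is not named.

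Protocol 12.4.2 has the same baseline terms and also adjusts for prognostic factors, with age and MMSE as examples. The SAP primary model does not carry these over.

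SAP 2.1.1 defines baseline explicitly only for safety evaluations. That the efficacy baseline is the Baseline visit alone is an inference from 2.5.5, where the average with Screening is called a new baseline.

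**The concern.** One cognitive test session is a noisy measure of a participant's pre-treatment level. A second pre-treatment session on the same instrument can remove some of that noise from the residual variance of the treatment contrast. It needs no new data and leaves the endpoint unchanged. Protocol 8.3.6 makes a related point when it says that day-to-day variability "may affect the accuracy of single-time point cognitive assessments".

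The one planned analysis that uses the Screening score also changes the post-treatment quantity, because Day 171 becomes an average over two visits. No named analysis therefore gives the unaltered week-24 contrast the benefit. At stake is precision in a trial that, according to SAP 1.1, stopped after 34 of a planned 86 participants were randomised.

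**Working it through.** **Inputs from the documents.** SD of change 0.38, difference 0.19, one-sided alpha 0.10, 36 evaluable per arm, 15% dropout (Protocol 12.8.1, SAP 3.1); 34 randomised (SAP 1.1). This is 17 per arm with no dropout, or about 14 per arm at 15% dropout (34 × 0.85 = 28.9 in total).

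**The plan's own figure.** The plan states that "data from 36 evaluable participants per arm (investigational agent and placebo) provides ~80% power". With power = Φ(Δ / (SD·√(2/n)) − 1.2816), n = 36 and SD = 0.38, differences of 0.19, 0.152, 0.114 and 0.095 give 79.95%, 66.1%, 49.7% and 41.3%. The stated 80, 66, 50 and 41% reproduce.

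**Assumed correlations.** The documents give none. If the five components have unit SD and mean inter-correlation r, the total has variance (1+4r)/5, and SD of change 0.38 implies ρ = 1 − 0.38²/(2·variance). For r = 0.2, ρ = 1 − 0.1444/0.72 = 0.80. For r = 0.6, ρ = 1 − 0.1444/1.36 = 0.89. A wider range is shown below.

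**Large-sample effect.** Write a for the correlation of Baseline with week 24, b for Screening with Baseline, and c for Screening with week 24. Adding Screening beside Baseline multiplies the residual variance by

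F = 1 − (c − ab)² / [(1 − a²)(1 − b²)].

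With a = b = c = ρ this is (1+2ρ)/(1+ρ)².

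**Small-sample cost.** In a single-visit ANCOVA with N participants in total, going from one random covariate to two multiplies the expected variance by (N−4)/(N−5). This is 30/29 = 1.034 at 17 per arm and 24/23 = 1.043 at 14 per arm. Simulation of the equal-correlation (0.7, 0.85), decay and unfavourable cases below agreed to within about 0.01.

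| a / b / c | F | 17 per arm | 14 per arm |
|---|---|---|---|
| 0.70 / 0.70 / 0.70 | 0.830 | 0.86 | 0.87 |
| 0.80 / 0.80 / 0.80 | 0.802 | 0.83 | 0.84 |
| 0.85 / 0.85 / 0.85 | 0.789 | 0.82 | 0.82 |
| 0.90 / 0.90 / 0.90 | 0.776 | 0.80 | 0.81 |
| 0.85 / 0.88 / 0.84 (decay) | 0.865 | 0.90 | 0.90 |
| 0.85 / 0.88 / 0.80 (decay) | 0.957 | 0.99 | 1.00 |
| 0.88 / 0.88 / 0.80 (unfavourable) | 0.987 | 1.02 | 1.03 |
| 0.85 / 0.85 / 0.7225 (nothing added) | 1.000 | 1.03 | 1.04 |

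**In power terms.** Take 0.38 as the residual SD of the one-baseline model and multiply it by the square root of the factor. At 36 per arm, 80% becomes 85-87% with equal correlations of 0.7 to 0.9 and 81-84% in the decay cases. At 17 per arm, 57% becomes about 61-63% with equal correlations of 0.7 to 0.85, 57-60% with decay, and 56% in the unfavourable case.

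**Repeated-measures check.** With five post-baseline visits, equal correlations and 15% monotone dropout, the large-sample ratio for the Day 171 contrast is 0.842 at ρ = 0.7, 0.803 at 0.85 and 0.790 at 0.9. The gain carries over to the MMRM almost unchanged.

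**A version that backfires.** Suppose change from the Baseline visit is kept but the only covariate is the Screening-Baseline average. The residual variance is then 2(1−ρ) − (1−ρ)²/[2(1+ρ)]. At ρ = 0.85 this is 0.2939 against 1 − ρ² = 0.2775, a ratio of 1.06. At ρ = 0.7 it is 0.5735 against 0.51, a ratio of 1.12. Both are worse than the planned model.

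**The case against.** The strongest case against has four parts.

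- **The gain depends on how well Screening predicts week 24.** Screening can precede Day 171 by about 230 days in a progressive disease, so equal correlations are the favourable case. This stands. A reader might infer a variance cut of 20% or more for this trial, or that the gain can never be negative. The documents support neither: they give no correlation, and at 14 to 17 per arm the extra term costs 3-4%, which can cancel a small gain.
- **One baseline covariate is conventional and unbiased, and the sponsor did plan a use of the Screening score.** This also stands. A reader might infer that the plan ignores the Screening score or that its primary analysis is wrong. SAP 2.5.5 rules out the first, and nothing in the documents supports the second. What remains is that 2.5.5 is supplementary and changes the post-treatment quantity.
- **The Protocol 12.4.2 model already lists age and MMSE.** MMSE is another pre-treatment cognitive measure and would absorb part of the gain if retained. The SAP primary model omits both, so the figures above apply to the model as the SAP now has it.
- **The remark in Protocol 8.3.6 is made in support of at-home testing and says only that accuracy may be affected.** It gives context. It does not say that the clinic NTB is unreliable.

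A practice effect from Screening to Baseline is not a strong objection. Both scores precede treatment, and an effect common to both arms does not bias the contrast.

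**Conclusion.** The point holds as an efficiency improvement. The primary week-24 contrast does not use a scheduled pre-treatment score that the plan itself treats as usable.

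- **Equal correlations:** variance falls about 17-22% in large samples (ρ 0.7 to 0.9), and about 13-18% at 14 to 17 per arm (ρ 0.7 to 0.85).
- **Correlation that decays with time:** about 4-14% in large samples, about 1-10% at the size reached.
- **Screening adds almost nothing beyond Baseline:** a loss of 2-3% at the size reached.

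Every figure rests on assumed correlations and on Screening scores being available as scheduled. The formula gives Screening its own coefficient at week 24. A single main effect loses nothing when correlations are equal, and may do slightly less well when they decay. The gain would not rescue the trial's power: at 17 per arm it stays near 60% on any of these assumptions.

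**What to change.** In SAP 2.5.1, before efficacy data are analysed by arm:

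- Add the Screening NTB total z-score, standardised with the same baseline mean and SD, as one main-effect covariate beside Baseline and baseline-by-visit. A by-visit version would add five terms, which suits 34 participants poorly in a model with unstructured covariance.
- Keep change from the Baseline visit and the Day 171 contrast. Do not adjust for the average alone while keeping change from Baseline.
- Where a Screening score is missing, use that participant's Baseline score.
- State that the efficacy baseline is the Baseline visit.

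The cost is one model degree of freedom and a documented departure from Protocol 12.4.2. The record should say when the change was made and that it was made without sight of efficacy results by arm, because Protocol Table 6-1 allows the statistician and programmers to be unblinded from the time the randomisation list is generated. The same entry should explain why age and MMSE were dropped from the primary model; if they are restored, expect a smaller gain from Screening. No new data are needed and the endpoint does not change.

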**Table 6-1** **Blinding levels**

Role	Time or Event			Commercially Confidential Information
	Randomization list generated	Treatment allocation & dosing	Safety event (single participant unblinded)	
Participants	B	B	B	
Site staff	B	B	B	
Unblinded site staff (see text for details)	NA	NA	NA	
Drug Supply and Randomization Office	UI	UI	UI	
Unblinded sponsor staff (see text for details)	UI	UI	UI	
Statistician/statistical programmer/data analysts	UI	UI	UI	
Independent committees used for assessing interim results	B	UI	UI	
All other sponsor staff not identified above	B	B	UI	

B Remains blinded

NA Not applicable

UI Allowed to be unblinded on individual patient level

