In addition, a sub-set of these same participants (up to 22 per investigational agent/matching placebo) will undergo PET CCI imaging at baseline and following completion of the first 12 weeks treatment. Alterations in activated microglia and astrocytes due to therapeutic intervention will be measured using a PET CCI PET imaging in this subset of participants and analysis of CSF and/or serum samples in all participants will provide measures of both central and peripheral inflammation following treatment with an investigational agent/matching placebo. An interim analysis of the PET CCI and CSF soluble biomarker data may be conducted following completion of the first 12 weeks of treatment.

For each investigational agent, one or more interim analyses may be conducted, as appropriate, to support decision making concerning the sponsor's clinical development projects in general, or in case of any safety concerns. The results of these analyses will not have any impact on study conduct.

The study design is described in Figure 1-1.

Figure 1-1 Study design schematic

B = Baseline R = Randomization EOC = End of cohort

Randomization for any participant can occur after informed consent is obtained and eligibility is confirmed, ideally as close to Day 1 as possible. Participants will be randomized into any of the treatment arms open to enrolment for which the participant meets the eligibility criteria

Treatment arm(s) will be defined for each cohort.

EOC2 visit only required for an extended half-life. For all other treatments, EOC1 will serve as End of Cohort visit.

Approximately n=86 participants were planned to be randomized in a 1:1 ratio (active:placebo) using an IRT system. The study was prematurely terminated after 34 participants randomized due to sponsor's decision.

The primary endpoint is the change in NTB total z-score at week 24.

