2.6.3 Statistical hypothesis, model, and method of analysis

Memory, cognition, executive function, and neuropsychiatric outcomes

The memory function composite score, the executive function composite score, the DSST score, the overall eCognitive test scores, the total ECog score and the average ECog score, and the total NPI and NPI-D scores will be analyzed using the same model as for the primary endpoint (See Section 2.5).

PET CCI

As only one participant has data available, the PET CCI data will be only listed.

Total CCI

For biotherapeutic agents, total ^{CCI} concentration data will be listed by treatment, participant, and visit/sampling time point. Summary statistics will be provided by treatment and visit/sampling time point.

In cohort 1, concentrations of serum and CSF total Commercially Confidential Information will be given in mass per volume units. Concentrations below the LLOQ will be reported as "zero".

Immunogenicity (Anti-ACZ885 Antibodies)

Summary statistics of the number of positive participants (n, %) will be provided by timepoint.

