3.1 Primary endpoint(s)

For the primary endpoint, change in NTB total z-score at week 24, data from 36 evaluable participants per arm (investigational agent and placebo) provides $\sim\!80\%$ power to detect a statistically significant difference between the two groups at a 1-sided $\alpha\!=\!0.10$ when the true standardized mean difference is 0.5. The effect size of 0.5 corresponds a moderate treatment effect which is thought to represent a clinically meaningful improvement at 24 weeks. To account for 15% dropout rate, approximately n=86 participants randomized in a 1:1 ratio would be needed to address the primary objective. These calculations take into account results of the published study by Frölich et al. (2019), where the standard deviation of the change in NTB total z-score was estimated to be $\sim\!0.38$ for both active and placebo groups.

For smaller true effect sizes, the power is lower (Table 3-1 below).

Table 3-1 Sensitivity of power to changes in assumptions

SD (common to 2 arms)	True mean difference (Δ)	True effect size (Δ/SD)	alpha (1-sided)	Power
0.38	0.19	0.5	10%	80%
0.38	0.152	0.4	10%	66%
0.38	0.114	0.3	10%	50%
0.38	0.095	0.25	10%	41%

It is assumed that n=86 participants are randomized in a 1:1 ratio and the dropout rate is 15% (thus we have 72 evaluable participants, 36 per arm)

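### Does the missing side and level for the week-24 primary p-value in SAP 2.5.1 leave the primary test open?

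*SAP*

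**What the plan says.** SAP 2.5.1 states the research hypothesis in one direction: "each investigated anti-inflammatory agent provides an improvement over placebo in NTB response at 24 weeks". It then describes the MMRM and its output: "Least squares mean, the associated 2-sided 90% confidence interval and the p-value will be obtained for each treatment at each visit". The next sentence fixes the comparison of interest: "The primary comparison will be the contrast between active treatment and placebo at 24 weeks". Protocol 12.4.2 has the same three elements. Neither section gives an alpha, a side for the p-value or a rule for reading the interval, and neither shows a redaction at that point.

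The level stands in the sizing sections. Protocol 12.8.1 says that 36 evaluable participants per arm "provides ~80% power to detect a statistically significant difference between the two groups at a 1-sided" alpha of 0.10. SAP 3.1 repeats it: "power to detect a statistically significant difference between the two groups at a 1-sided" 0.10. SAP 2.5 adds that a positive change in the NTB z-score is an improvement, which settles which tail is meant.

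SAP 1.1 records the state of the trial: "The study was prematurely terminated after 34 participants randomized", against about 86 planned.

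**The concern.** A programmer working from SAP 2.5.1 alone sees an unlabelled p-value beside an interval described as two-sided. That interval does not match the sizing test. A two-sided 90% interval excludes zero on the favourable side when a one-sided 0.05 test rejects; the interval matching a one-sided 0.10 test is a two-sided 80% one. The p-value could therefore be produced or read as two-sided although the trial was sized on a one-sided test. SAP 2.6.3 applies the same model to the memory, executive function, DSST, eCognitive, ECog and NPI outcomes, so the missing label carries over.

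Timing adds to the worry. The SAP was written after termination and with some data availability known; on PET it says "As only one participant has data available". Protocol Table 6-1 lets the row "Statistician/statistical programmer/data analysts" be unblinded at individual level. If the side were really open, it could be chosen once results by arm had been seen. At this sample size that choice could move the p-value across 0.10 at the plan's own target difference.

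**Working it through.** **1. Which test was the trial sized on?** Inputs from SAP 3.1 and Table 3-1 (the same in Protocol 12.8.1 and Table 12-1): n = 36 per arm, SD 0.38, alpha 0.10. With SE = SD·√(2/n) = 0.38·√(2/36) = 0.0896, the normal approximation is power = Φ(Δ/SE − z). Here z = 1.282 for one-sided 0.10 and 1.645 for two-sided 0.10. For Δ = 0.19: Δ/SE = 2.121, so power is Φ(0.840) = 79.9% one-sided and Φ(0.476) = 68.3% two-sided.

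| Δ (z units) | Stated | One-sided 0.10 | Two-sided 0.10 |
|---|---|---|---|
| 0.19 | 80% | 79.9% | 68.3% |
| 0.152 | 66% | 66.1% | 52.1% |
| 0.114 | 50% | 49.7% | 35.5% |
| 0.095 | 41% | 41.3% | 28.0% |

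All four rows fit the one-sided test and none fits the two-sided one. The sample size agrees too: 36/0.85 = 42.4, so 43 per arm and 86 in total.

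**2. How much could the label change?** The documents give neither the arm split nor the number evaluable at week 24. Assume equal arms, SD 0.38 and an unadjusted two-sample t-test, with an observed difference of 0.19 z. At 17 per arm:

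- SE = 0.38·√(2/17) = 0.1303; t = 0.19/0.1303 = 1.458 on 32 df; p = 0.077 one-sided, 0.155 two-sided.
- Smallest difference reaching p < 0.10: 1.309 × 0.1303 = 0.171 z one-sided; 1.694 × 0.1303 = 0.221 z two-sided.
- Two-sided 90% interval: 0.19 ± 0.221, that is −0.031 to 0.411. The lower limit of the 80% interval is 0.019.

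**3. How far does that illustration carry?** All rows are for an observed 0.19 z.

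| Per arm | SD | p one-sided | p two-sided | Label decides at 0.10? |
|---|---|---|---|---|
| 17 | 0.38 | 0.077 | 0.155 | yes |
| 14 | 0.38 | 0.099 | 0.197 | yes, barely |
| 13 | 0.38 | 0.107 | 0.215 | no, both above |
| 17 | 0.30 | 0.037 | 0.074 | no, both below |
| 17 | 0.34 | 0.057 | 0.113 | yes |
| 17 | 0.42 | 0.098 | 0.197 | yes |
| 17 | 0.45 | 0.114 | 0.227 | no, both above |

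Before any data are seen, the chance of landing between the two cut-offs at 17 per arm is 0.563 − 0.414 = 0.149 for a true effect of 0.5 SD, and 0.10 − 0.05 = 0.05 under the null.

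**4. Is 17 per arm realistic?** It is the upper end. The primary analysis uses the PD analysis set (SAP 2.5), and SAP Table 2-1 already removes one participant from it. Protocol 9.1.1 counts stopping treatment as leaving the study, and Protocol 9.5 has participants handled as early withdrawals if the sponsor ends the study. The MMRM also adjusts for baseline, so its effective SD is not known from the documents.

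**The case for a change.** The best case for a change is that an analysis section should stand on its own. Protocol 4.3 says each agent's success depends on a positive NTB result, and the visible text never says what counts as positive. One added sentence would cost almost nothing, and it would be worth most in a SAP finalised after the trial stopped.

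Part of this stands. Sections 2.5.1 and 12.4.2 do omit the side and level, and the 90% interval is not the counterpart of a one-sided 0.10 test. Anyone who treats that interval excluding zero as the design criterion would be applying a stricter rule than the one used for sizing.

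The rest is weaker. The sentence would only restate what SAP 3.1 already says for this endpoint, and the visible text offers no rival level: the one-sided 0.05 elsewhere is for PET sizing. The worry about a late choice has little to act on, because the alpha and the output sentence both stand in a protocol that still plans 86 participants. Protocol 6.4 describes the statistician's access to the randomization list as being for interim analyses, and SAP Section 4 says the planned interim will not be conducted. SAP 2.13 does have the trial statistician and programmers run the DMC analysis, so access is possible, but nothing shows that NTB results by arm were reviewed.

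An added sentence that kept the 90% interval would also leave the mismatch in place: at 0.19 z and 17 per arm the table would show p = 0.077 beside an interval that includes zero.

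**Conclusion.** This is missing detail that an analyst fills sensibly from the same document. The directional hypothesis, the stated direction of improvement and the one-sided 0.10 in SAP 3.1 leave one natural reading, and the plan's power table confirms it in all four rows. No passage makes the 90% interval a success criterion; read literally, it belongs to each arm's least squares mean.

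Under either label the model, data, estimate, interval and stated power are identical. A reader with the estimate and its sign can convert one p-value to the other by a factor of two. For a stopped Phase IIa trial with 34 randomized, no visible decision depends on crossing 0.10. The label would decide only in a narrow case: an observed difference near 0.19 z, about 14 to 17 per arm, an SD near 0.38 and an unadjusted test.

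Two limits apply. The arm split and week-24 numbers are not given, so the p-values are illustrations. Parts of the text on interim analyses and missing data are redacted, so a decision rule there cannot be excluded.
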